**Research on the Construction of a Prognostic Model for COPD
Complicated with Sarcopenic Obesity Based on Bioelectrical
Impedance Phase Angle Technology (COSAT)**

Research Protocol

Main researchers: [name], [name]

Clinical research department: Respiratory and Critical Care

Medicine Sponsor: [name]

Ethics Review No.:2025K200

Scheme Version No: 01

Plan Preparation date: July 15th, 2025

Research Objectives:

This study aims to explore the diagnosis, impact, and prognostic factors of COPD complicated with sarcopenic obesity using multi-segment bioelectrical impedance phase angle technology. It seeks to clarify the diagnostic value and efficacy of body composition analysis in specific populations, analyze the relationship between phase angle and COPD severity as well as quality of life, investigate its predictive role for adverse outcomes, and reveal the effects of inflammation and metabolic disorders in sarcopenic obesity. The goal is to provide a basis for early screening and precise intervention to improve patient prognosis.

Proposed Research Methods

Inclusion Criteria

- (1) Age over 65 years;**
- (2) Ability to complete physical activity assessments and pulmonary function tests;**
- (3) Complete medical records, willingness to adhere to follow-up arrangements, and provision of adverse event reports via telephone or outpatient visits, with signed informed consent;**
- (4) COPD diagnosis based on the American Thoracic Society (ATS)/European Respiratory Society (ERS) GOLD definition, with a post-bronchodilator FEV1/FVC ratio < 0.70, current or former smokers with a smoking history of ≥ 10 pack-years.**

Exclusion Criteria:

- (1) Severe cognitive impairment or hand deformities (e.g., rheumatoid arthritis) preventing body composition measurements;**
- (2) Incomplete clinical or follow-up data or unwillingness/inability to undergo regular follow-up;**
- (3) Severe systemic edema;**
- (4) Presence of cardiac pacemakers or significant metal implants that may interfere with measurements;**
- (5) Voluntary withdrawal for any reason, including loss to follow-up.**

Data Collection:

Demographic and clinical data: Gender, smoking status (never, former, current), age, height, weight, waist circumference, BMI, skeletal muscle index (SMI), body fat content,

visceral fat index, and segmental phase angles measured via bioelectrical impedance analysis.

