Clinical records: Smoking history, comorbidities (Charlson Comorbidity Index), nutritional status (MNA-SF), physical performance (SPPB), medication use, pulmonary function tests, COPD exacerbations in the past year, CAT score, mMRC score, and St. George's Respiratory Questionnaire (SGRQ).

Laboratory tests: Blood samples for CBC, CRP, cholesterol, albumin, HbA1c, IL-6, and TNF- α (ELISA).

Sample Size Calculation:

Using PASS 15.0 for repeated-measures ANOVA ($\alpha = 0.05$, power = 90%), with a COPD prevalence of 15% and a 2:1 ratio for sarcopenic obesity vs. non-sarcopenic groups, the study requires 200 participants (33 sarcopenic obese, 33 non-obese sarcopenic, 72 obese non-sarcopenic, and 72 non-obese non-sarcopenic).

Diagnostic Criteria:

Sarcopenia: Asian Working Group criteria: SMI (InBody S10) $<7.0 \text{ kg/m}^2$ (men) or $<5.7 \text{ kg/m}^2$ (women); grip strength $<28 \text{ kg}$ (men) or $<18 \text{ kg}$ (women); gait speed $<0.8 \text{ m/s}$. **Obesity:** BMI $\geq 28 \text{ kg/m}^2$ or waist circumference $\geq 85 \text{ cm}$ (men)/ $\geq 80 \text{ cm}$ (women); body fat $\geq 24.3\%$ (men) or $\geq 33.2\%$ (women).

sarcopenic Obesity: Coexistence of sarcopenia and obesity.

Assessments:

Physical Performance: Short Physical Performance Battery (SPPB: balance, gait speed, chair stands; score 0–12).

Nutritional Status: Mini Nutritional Assessment (MNA-SF; score 0–12).

Phase Angle: Measured via InBody S10 at six frequencies (1kHz–1000kHz) across five body segments, calculated using resistance (R) and reactance (Xc):

$\text{PHA} = \arctan((\text{Xc_right arm} + \text{Xc_trunk} + \text{Xc_right leg}) / (\text{R_right arm} + \text{R_trunk} + \text{R_right leg})) \times 180^\circ / \pi$.

Follow-up Endpoints:

Primary: Changes in pulmonary function, dyspnea scores, and body composition at 2 years.

Secondary: Acute exacerbations, hospitalizations, or death within 2 years. Follow-ups at 6, 12, and 24 months.

Grouping patients based on whether they have sarcopenic obesity, the differences in clinical data between the two groups were analyzed. Statistical analysis was performed using SPSS 24.0 statistical software.

Analysis of Demographic Characteristics and Clinical Data:

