The age and gender distribution of the patients were described. Based on whether the patients had sarcopenic obesity, they were divided into two groups. The differences in clinical data between the two groups, including age distribution, smoking status, obesity-related body fat, pulmonary function, whole-body and segmental phase angle, were analyzed. Continuous variables were expressed as mean \pm standard deviation, and categorical variables were expressed as percentages. Differences between groups were analyzed using Student's t-test for continuous variables and the chi-square test for categorical variables, depending on the data type.

Analysis of Factors Associated with COPD Complicated by Sarcopenic Obesity:

Univariate and multivariate analyses were conducted on data from COPD patients with sarcopenic obesity. Using clinical data variables, nutritional status, physical activity capacity, whole-body and segmental phase angle, logistic regression was applied to analyze the factors associated with sarcopenic obesity in COPD patients.

Analysis of the Prognostic Predictive Value of Sarcopenic Obesity in Obstructive Pulmonary Disease:

The differences in hospital stay length, acute exacerbation readmission rate, and mortality between COPD patients with sarcopenic obesity and those without sarcopenia at baseline were compared. Kaplan-Meier analysis was used for statistical analysis, and differences were expressed using the log-rank test.

COSAT study

INFORMED CONSENT FORM

This document provides you with information to help you decide whether to participate in this clinical research study. Please read it carefully. If you have any questions, please direct them to the researcher in charge of this study.

Your participation in this study is voluntary. This research has been reviewed and approved by the institutional ethics review committee of our research institution.

The background, objectives, research process, and other important information are as follows:

Research Purpose:

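### The sample-size statement contradicts itself: the four groups add to 210, not 200, the 2:1 ratio is reversed, and the 90% power belongs to a test the analysis text never names

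*Combined protocol and SAP*

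**What the plan says.** The Sample Size Calculation section is one sentence. It begins "Using PASS 15.0 for repeated-measures ANOVA", sets alpha at 0.05 and power at 90%, continues "with a COPD prevalence of 15% and a 2:1 ratio for sarcopenic obesity vs. non-sarcopenic groups", and concludes that "the study requires 200 participants (33 sarcopenic obese, 33 non-obese sarcopenic, 72 obese non-sarcopenic, and 72 non-obese non-sarcopenic".

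Under Follow-up Endpoints the primary endpoint is "Changes in pulmonary function, dyspnea scores, and body composition at 2 years", and the visit schedule is "Follow-ups at 6, 12, and 24 months".

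The analysis text divides patients into two groups, with and without sarcopenic obesity. For the clinical data it says "Differences between groups were analyzed using Student's t-test for continuous variables and the chi-square test for categorical variables". It uses logistic regression for factors associated with sarcopenic obesity. For prognosis it says "Kaplan-Meier analysis was used for statistical analysis, and differences were expressed using the log-rank test", comparing patients who have sarcopenic obesity with those who had no sarcopenia at baseline.

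The Inclusion Criteria require a COPD diagnosis. The Exclusion Criteria include "Voluntary withdrawal for any reason, including loss to follow-up".

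**The concern.** One sentence has to settle how many patients are planned, in what proportions, and for which test. It does not settle any of these. The total disagrees with its parts, the ratio runs against the listed groups, and the named test does not reappear in the analysis text. One input, a COPD prevalence of 15%, has no evident role in a study where every participant must have COPD.

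Two things are at stake. The study has no single recruitment target. The primary endpoint also carries a power claim without an analysis tied to it, so the choice among a t-test on 2-year change, a repeated-measures model with two groups or one with four could be made after the data are seen.

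**Working it through.** **1. Total.** From the stated groups, 33 + 33 + 72 + 72 = 210. The difference from 200 is 10, and 10/200 = 5%, too much for rounding. The documents do not show where the slip is:

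| Groups | Total | Cell ratio |
|---|---|---|
| 33/33/72/72 (as listed) | 210 | 72/33 = 2.18 |
| 33/33/67/67 (keep 200 and the 33s) | 200 | 67/33 = 2.03 |
| 28/28/72/72 (keep 200 and the 72s) | 200 | 72/28 = 2.57 |

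A 5% allowance would also link the two figures (200 × 1.05 = 210), but no dropout rate is stated.

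**2. Ratio.** Sarcopenic to non-sarcopenic, from the listed groups:

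- cell against cell: 33:72 = 1:2.18
- all sarcopenic against all non-sarcopenic: 66:144 = 1:2.18
- sarcopenic obese against all non-sarcopenic: 33:144 = 1:4.36

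The non-sarcopenic side is larger each time. Read literally, 2:1 on 200 would give about 133 against 67. Even when reversed, the listed groups are not exactly 1:2.

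**3. Powered test against planned tests.** The calculation uses four groups and a repeated-measures ANOVA. The analysis text uses two groups and names a t-test, a chi-square test, logistic regression, Kaplan-Meier and the log-rank test. Repeated-measures ANOVA appears only in the sample-size sentence. The t-test paragraph mentions neither change from baseline nor the follow-up visits.

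**4. Can the 90% be reproduced?** No. Effect size, SD, within-patient correlation, number of time points and the tested effect are all absent. To show how far they decide the answer, *assume* a group-by-time test with four groups, four time points (baseline plus the three visits), f = 0.10 and sphericity. Then df1 = (4 − 1)(4 − 1) = 9, df2 = 3(N − 4), and the noncentrality is λ = f² × N × 4/(1 − ρ):

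| Assumed correlation ρ | N for 90% power | Power at N = 200 |
|---|---|---|
| 0.3 | 350 | 63% |
| 0.5 | 251 | 80% |
| 0.7 | 152 | 97% |
| 0.9 | 53 | over 99% |

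A simulation with equal groups at N = 352, 252, 152 and 52 gave power of 0.91, 0.92, 0.91 and 0.89, in line with the formula.

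**5. The two-group t-test, for illustration.** Take the listed groups as sarcopenic obese against all others, 33 v 177 (33 + 72 + 72), two-sided 0.05. The normal approximation to the standardised difference detectable with 90% power is (1.960 + 1.282) × √(1/33 + 1/177) = 0.61. The noncentral t distribution gives 0.617, and power of 0.747 at a difference of 0.5. With a total of 200 (33 v 167) the detectable difference is 0.62; against non-sarcopenic patients only (33 v 144) it is 0.63. Applying an assumed loss to the 33 v 177 split:

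| Assumed loss | Groups | Detectable difference |
|---|---|---|
| 10% | 30 v 159 | 0.649 |
| 20% | 26 v 142 | 0.696 |
| 30% | 23 v 124 | 0.741 |

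**6. Enrolled or evaluable.** Loss to follow-up is listed as an exclusion, so the total could mean either. The figures below run from 10% to 30% loss.

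| Stated total | If enrolled, patients remaining | If evaluable, patients to enrol |
|---|---|---|
| 200 | 180 to 140 | 200/0.9 = 223 to 200/0.7 = 286 |
| 210 | 189 to 147 | 210/0.9 = 234 to 210/0.7 = 300 |

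**The case against.** - **The slips are small.** This is an observational cohort in which group membership is measured, not allocated. A 5% discrepancy and a reversed label may be drafting errors, and nothing shows that 200 or 210 is inadequate. That is fair as to size. The recruitment target and proportions are still contradictory as written.
- **A test is arguably named.** The t-test paragraph covers pulmonary function, body fat and phase angle, which touch two of the three primary domains. This stands in part: the defensible statement is that no test is tied to change at 2 years. Even if the t-test was meant for the primary endpoint, it is not the test that was powered.
- **The 15% may be real but mislabelled.** The sarcopenic obese share is 33/210 = 15.7% or 33/200 = 16.5%, so 15% could be an expected share of sarcopenic obesity. This is conjecture, but it is a good reason to trace the input before deleting it.
- **The ANOVA illustration rests on assumptions.** That is correct. The range of 53 to 350 shows only that the missing inputs decide the answer; it does not measure an error in the plan.

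**Conclusion.** The point holds. The sample-size sentence cannot be true as written: its groups exceed its total by 10 patients (5%), and its ratio is reversed under every pairing. Both follow from the sentence alone and need no assumption. The mismatch between a four-group repeated-measures ANOVA and two-group tests follows from comparing that sentence with the analysis text. The protocol text available runs up to the start of the consent form, and the claim that the powered test is named nowhere else is limited to that text.

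The 90% power is neither confirmed nor refuted. The illustrative sample sizes and detectable differences depend on the assumed f, correlations, time points and loss rates. Correction is needed because the study relies on this total, ratio and power basis.

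**What to change.** 1. Recover the PASS inputs and restate one total, one set of group sizes that adds to it, and one ratio in the right direction.
2. Trace the 15% prevalence. Relabel it if it stands for something else; remove it if it played no part.
3. Make the powered test and the primary analysis agree. Either name the repeated-measures model (group, time and group-by-time) as the analysis of 2-year change, saying whether group has two levels or four, or restate power for the test that will be used.
4. Give the power or detectable difference with its effect size, SD, within-patient correlation and expected attrition. Say whether the total counts enrolled or evaluable patients.
5. State that the 90% does not apply to the secondary survival comparisons.

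The drafting cost is one rewritten paragraph and one sentence naming the primary analysis. Because the plan has ethics approval, naming that analysis or changing the total probably needs an amendment. The stated power may become less favourable and the total may change once the inputs are recovered.

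### The 90% power at 200 participants carries no stated allowance for loss, while exclusions (2) and (5) can remove participants after enrolment

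*Combined protocol and SAP*

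**What the plan says.** Under *Sample Size Calculation* the protocol names the method ("Using PASS 15.0 for repeated-measures ANOVA") with alpha 0.05 and power 90%, and concludes that "the study requires 200 participants", divided into "33 sarcopenic obese, 33 non-obese sarcopenic, 72 obese non-sarcopenic, and 72 non-obese non-sarcopenic". The only other inputs are given as "with a COPD prevalence of 15% and a 2:1 ratio for sarcopenic obesity vs. non-sarcopenic groups". It gives no effect size, standard deviation, within-subject correlation, number of time points or expected loss, and does not say whether 200 counts people enrolled or people evaluable.

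Under *Exclusion Criteria*, item (2) is "Incomplete clinical or follow-up data or unwillingness/inability to undergo regular follow-up" and item (5) is "Voluntary withdrawal for any reason, including loss to follow-up".

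Under *Follow-up Endpoints*, the primary endpoint is change in lung function, dyspnoea scores and body composition at 2 years, with visits at 6, 12 and 24 months. Death belongs to the other endpoint set: "Secondary: Acute exacerbations, hospitalizations, or death within 2 years".

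The analysis sections name the t-test, chi-square test, logistic regression, and Kaplan-Meier curves with a log-rank test. The text available gives no missing-data method and no rule for replacing participants.

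**The concern.** A 2-year change needs a 24-month measurement. The population is COPD patients over 65, and the protocol plans to compare mortality, so it expects some deaths. It also expects withdrawal and loss, since it has written rules for them. Those rules work as exclusions even though the events can happen only after a person has joined.

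Two things follow. First, if 200 people are enrolled and the rules are applied, the analysed number is smaller than the number to which the 90% is attached. A non-significant primary result could then be read as coming from a 90%-powered study when the true figure is lower. Second, the people removed are chosen by what happened to them during follow-up. The analysed set is therefore selected as well as smaller, and the 6- and 12-month data of those later lost are discarded.

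**Working it through.** **1. Can the plan's own figure be reproduced?** No. Without an effect size, standard deviation, correlation or tested term, neither 200 nor 90% can be derived. The group sizes also disagree with the total: 33 + 33 + 72 + 72 = 210, which is 10 (5%) more than 200.

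**2. What can be calculated.** Power after loss needs no effect size if the effect is fixed at whatever value gives exactly 90% at 200 complete participants. That anchor is an assumption, made in the sponsor's favour. The loss proportion d is also assumed, because the documents give none. Alpha is taken as two-sided 0.05.

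**3. Two-group normal approximation.** Power = Φ((1.960 + 1.282)·√(1 − d) − 1.960), using the unrounded sum 3.2416.

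- d = 0.10: Φ(3.2416 × 0.9487 − 1.960) = Φ(1.115) = 86.8%
- d = 0.20: Φ(3.2416 × 0.8944 − 1.960) = Φ(0.939) = 82.6%
- d = 0.30: Φ(3.2416 × 0.8367 − 1.960) = Φ(0.752) = 77.4%

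**4. Check by non-central F.** The non-centrality is N·f², with f solved to give 90% at N = 200: f = 0.230 for two groups and 0.269 for four. Replacing N by N(1 − d) gives the results below. The last two columns keep the same f but start from 210 enrolled, leaving 189, 168 and 147 at losses of 10%, 20% and 30%.

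| Assumed loss | 200 enrolled, 2 groups | 200 enrolled, 4 groups | 210 enrolled, 2 groups | 210 enrolled, 4 groups |
|---|---|---|---|---|
| 5% | 88.5% | 88.3% | 89.9% | 89.9% |
| 10% | 86.7% | 86.3% | 88.3% | 88.1% |
| 20% | 82.5% | 81.5% | 84.3% | 83.5% |
| 30% | 77.2% | 75.3% | 79.2% | 77.6% |

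**5. The rules set side by side.** Exclusion (5), and the follow-up-data part of exclusion (2), cannot be assessed at enrolment. Read literally, they take out people who were already in the study. Death is different. It counts as an event in the secondary analysis and removes nobody from it, but it leaves the primary 2-year change undefined.

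**The case against.** A reader might go further and infer that the 200 assumes complete 2-year data in everyone, and that the 90% is therefore wrong. The documents do not support that. Nothing says that 200 is the enrolled number. It could be an evaluable target, with excluded people not counted towards it, or it could already hold an unreported allowance. The listed 210 equals 200 × 1.05, which would fit a 5% margin; it would equally fit an adding error. Without the effect inputs, the 90% can be neither confirmed nor refuted. At 5% loss the drop is under 2 points, and at 10% only 3 to 4. All of this stands, and it makes the size of the problem conditional.

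It does not remove the point. If 200 is evaluable, the enrolment target is missing. If 210 is a margin, the text does not say so, and power still falls below 90% at losses of 10% or more. Nothing in the protocol supports a loss as low as 5% over two years.

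A reader might also infer a harsher figure from the named method. If repeated-measures ANOVA used only people seen at every visit, independent 10% missingness at each of three visits would leave 0.9³ = 72.9% complete. That method is named only for the sample size, however, and is not restated as an analysis, so this scenario should not be charged to the plan.

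Finally, it is fair to say that the missing effect inputs, the 200/210 mismatch, and a stated 2:1 ratio that runs opposite to the listed groups (66 sarcopenic to 144 non-sarcopenic, about 1:2.2) are more basic faults in the same section. They should be corrected together with this one.

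**Conclusion.** The point holds in conditional form. The protocol attaches 90% power to 200 participants, states no allowance for loss, and has exclusion rules that shrink and select the analysed set after enrolment. The 90% is unsupported for that set; it has not been shown to be false.

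If 200 is the enrolled number and gives exactly 90% with complete data, power is about 86-87% at 10% loss, 82-83% at 20% and 75-77% at 30%. If 210 are enrolled and 200 complete participants give 90%, it is about 88%, 84% and 78-79%. The loss rates are assumptions, and these figures concern only the primary 2-year changes. The selection produced by exclusions (2) and (5) is a problem whichever number is right.

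**What to change.** (a) In *Sample Size Calculation*, reconcile 200 with 210 and say which number is enrolled and which is evaluable. State that the 90% applies to participants with 24-month data, after confirming this against the PASS run and giving its effect inputs. Report the power at the 2-year loss the sponsor expects. No added enrolment is needed for this.

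(b) Limit exclusions (2) and (5) to facts known at enrolment, so that later withdrawal, loss or incomplete follow-up does not remove a participant. Without this change, (c) cannot be carried out as described.

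(c) Specify a linear mixed model, available in SPSS, for the primary changes. Use all 6-, 12- and 24-month data from every enrolled participant, and report deaths alongside, since the model does not give a person who has died a meaningful 2-year value. The complete-data power figures then serve as a cautious guide, because partial follow-up recovers some information.

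The cost is a few sentences of protocol and analysis wording, a slightly less favourable stated power, a little more analysis work, and reliance on a missing-at-random assumption, which should be stated.

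### Three primary domains have no named variable, order, success rule or multiplicity plan, and the single alpha and power statement is tied to none of them

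*Combined protocol and SAP*

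**What the plan says.** The Follow-up Endpoints section of the protocol has one primary line: "Primary: Changes in pulmonary function, dyspnea scores, and body composition at 2 years". Visits are at 6, 12 and 24 months. No lung-function index, dyspnea scale or body-composition measure is singled out.

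The Data Collection section shows what could fill each domain. For body composition it lists "waist circumference, BMI, skeletal muscle index (SMI), body fat content", together with weight, a visceral fat index and segmental phase angles. For lung function and symptoms it lists "pulmonary function tests, COPD exacerbations in the past year, CAT score, mMRC score, and St. George's Respiratory Questionnaire (SGRQ", without saying which scales are the dyspnea scores or which lung-function index is meant.

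Alpha and power appear once, under Sample Size Calculation: "Using PASS 15.0 for repeated-measures ANOVA", with alpha 0.05 and power 90%. The result is given as "the study requires 200 participants (33 sarcopenic obese, 33 non-obese sarcopenic, 72 obese non-sarcopenic, and 72 non-obese non-sarcopenic". That sentence names no endpoint, effect size, standard deviation (SD) or within-subject correlation.

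The analysis sections describe t-tests, chi-square tests, logistic regression and Kaplan-Meier curves with a log-rank test. They state no significance level, mention no multiplicity adjustment and assign no explicit test to the 2-year changes. The repeated-measures ANOVA does not reappear. The sample size uses four groups, whereas the main comparison is between two (with and without sarcopenic obesity).

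**The concern.** A primary endpoint should fix in advance which result answers the study question. Here a significant change in any lung-function index, symptom score or body-composition measure could later be reported as the primary result, and nothing in the plan would contradict that. The reader could not tell how many comparisons stood behind it.

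Two things are at stake. First, if any one success is enough, the chance of a false primary finding exceeds the 0.05 used for the sample size. Second, the 90% power belongs to no identifiable endpoint or contrast, so nobody can say what the study is powered to detect.

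**Working it through.** **The plan's own figure.** The total of 200 cannot be reproduced, because the effect size, SD, within-subject correlation and dropout are not given. (The listed groups sum to 33 + 33 + 72 + 72 = 210, which is a separate matter to reconcile.) The check below therefore concerns the error rate and power across the primary set, not the sample size itself.

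**Inputs.**
- Number of domains: 3 (Follow-up Endpoints).
- Alpha 0.05 and power 90% (Sample Size Calculation). Sidedness is not stated; two-sided is assumed.
- Number of tests per domain: not stated. One per domain is the minimum case; 6 and 9 in total are assumptions for illustration.
- Correlation between test statistics: not stated. The range 0 to 0.9 is shown.
- Success rule: not stated. Both possibilities are worked through.

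**If any one significant result counts.** For k independent tests the chance of at least one false positive is 1 − 0.95^k. With k = 3 this is 1 − 0.857 = 14.3%. For correlated tests, the figures come from equicorrelated normal test statistics, each compared with ±1.96:

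| Tests | Independent | Correlation 0.5 | Correlation 0.9 |
|---|---|---|---|
| 3 (one per domain) | 14.3% | about 12.5% | about 8% |
| 6 (assumption) | 26.5% | about 21% | about 11% |
| 9 (assumption) | 37.0% | about 27% | about 12% |

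**If all three must be significant.** The chance of a false overall claim does not exceed 5%, because at least one true null hypothesis must be rejected at 0.05. The cost is power. If each test had 90% power and the three were independent, joint power would be 0.90³ = 72.9%. Positive correlation raises this, but it reaches 90% only if the tests are in effect identical or some of them have more than 90% power.

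**Cost of the possible remedies.** A 90% test at two-sided 0.05 corresponds to a standardised effect of 1.960 + 1.282 = 3.242.
- Bonferroni over three, or the strictest step of Holm, uses 0.05/3 = 0.0167, with critical value 2.394. Power becomes Φ(3.242 − 2.394) = Φ(0.848), about 80%. Keeping 90% under Bonferroni would need ((2.394 + 1.282)/(1.960 + 1.282))² = 1.29 times the sample.
- A fixed testing order keeps 0.05 for the first endpoint, so that endpoint loses no power.

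The 90% in these comparisons is a reference value. The documents do not show that any particular endpoint has it.

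**The case against.** A reader might infer that the protocol commits to testing every primary variable at 0.05, and so breaks a 5% study-wide error rate that it promised. The documents do not support that. The 0.05 is only a sample-size input, no level is set for the primary changes, and no familywise rate is claimed. Nor do they show that every domain holds several variables. The list is explicit for body composition only; the lung-function indices are not listed and the dyspnea scale is not named. The true number of tests is therefore unknown.

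It is also fair to say that the inflation depends on an any-one-counts rule that the protocol never states, and that high correlation among weight-related measures would limit it. The study is observational, assigns no intervention and describes its aim as exploratory, so strict familywise control is partly a matter of judgement.

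These points make the error-rate figures conditional and limit how serious the matter is. They do not remove the gap. The protocol labels endpoints as primary, states a power, and hopes to inform screening and intervention, yet it does not say which result the alpha and power describe. Under either success rule, the stated pair does not in general hold for the primary set.

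**Conclusion.** The concern holds in conditional form. The primary outcome is three undefined domains with no variable, order, success rule or multiplicity plan, and the alpha and power statement is attached to none of them.

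If each domain is tested once at two-sided 0.05 and any one result counts, the chance of a false primary finding is about 8% to 14%, depending on correlation. More tests raise it, but any count above three is an assumption. If all three must succeed, the error rate is not inflated and the loss is in joint power. Because the study is exploratory and observational, this is something the sponsor should correct, not a defect that invalidates the design.

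**What to change.** Before follow-up data are analysed, amend the Follow-up Endpoints and analysis sections as follows:

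1. Name one primary variable, the 24-month time point, the group contrast and the test. The choice is the sponsor's. Change in FEV1 from baseline, compared between patients with and without sarcopenic obesity, is only an example.
2. Name one dyspnea score and one body-composition variable, to be tested next in that fixed order, each at two-sided 0.05 and only if the preceding test is significant.
3. Report all other variables with confidence intervals and label them exploratory.
4. Restate the power for the named primary at the planned sample size, once the total of 200 and the groups summing to 210 are reconciled, with an explicit effect size, SD and within-subject correlation. The 90% cannot be carried over by rewording, because the inputs behind it are not given.

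The cost is an amendment and a new power calculation, with no extra measurements. The downsides are that fewer variables can be called primary, a failed first test blocks formal claims on the later ones, and the restated power may be less than 90%.
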